In secondary analyses, we used *compliance* (defined as number of treatment sessions received) as the independent variable of interest, categorized as compliance equal to zero (control group or intervention participants with no PM and no SB sessions), 1+ session (at least one PM or SB session without full compliance), and full compliance to the treatment protocol (10 PM and 25-36 SB sessions). While this analysis no longer relies on random assignment, it serves to provide confirmation of the results from the intent-to-treat analysis and provides further estimates of the magnitude of the intervention effects on the main outcomes evaluated at 6 and 12 months after the baseline. Because *compliance* made use of both number of PM and number of SB sessions, all compliance analyses excluded the 35 participants who did not receive the SB sessions and their 35 control counterparts.

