To decrease barriers to engagement in the combined intervention, we designed the program to be deliverable both in person and over the phone. Study participants assigned to receive the Strong Bodies intervention were offered an instructional video of the exercises for at-home use. If participants were unable to attend the small-group exercise sessions in-person 3 times per week for 12 weeks, they received training from their Exercise Trainer to use the instructional video and perform the exercises at home. The video was intended to supplement the in-person classes and provide an opportunity for participants to engage in exercises when they are unable to attend the class in person. To this end, we discussed important considerations for phone delivery during the training of study clinicians. For instance, we discussed the need to ask participants whether they were in a private place with no distractions, the importance of vocal intonation, referring to the participant manual, and verbal affirmations to convey empathy.

Community Health Workers (CHWs) deliver the Positive Minds component of the intervention. We drew on the Bureau of Labor Statistics model of CHWs who "implement programs in the community that promote, maintain, and improve individual and community health" (Standard Occupational Classification 21-1094 Community Health Workers. 2017; <https://www.bls.gov/oes/2017/may/oes211094.htm>)

CHWs were selected and trained from each collaborating community-based organization (CBO) and the Disparities Research Unit. Each CBO had a designated site leader who oversaw the intervention process locally. Part of the Site Leaders' role was to identify staff – either within the organization or identified externally – who would carry out the CHW position. Our recruitment criteria included identifying individuals with work experience that was relevant to the intervention; who were bilingual/bicultural; and who exhibited interpersonal skills in communication, trust, warmth and rapport-building.

We devoted significant time to training the CHWs to offer the clinical intervention at the study sites. Over a four-month period, they were trained on the core elements of the intervention and on understanding the skills and objectives of the intervention. CHWs began with a 2-day training including didactic instruction and role play. The training included two intensive days of workshops and practice sessions, including

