Since the time variable is centered at 6-month follow-up, the beta coefficient on  $Intervention_i$  can be interpreted as the treatment effect on outcome levels evaluated at the end of the intervention. That is, testing for the significance of  $\beta_1$  tests the hypothesis that the treatment was more effective than enhanced usual care in improving the outcomes, as evaluated at 6 months after the baseline. The coefficient of intervention by time interaction  $\beta_3$ , tests whether the pattern of outcomes over time would be no different between treatment and enhanced usual care groups. Similarly,  $\beta_5$  tests whether changes in outcome responses over time were different between treatment and control groups after the intervention had ended. The constant term  $(\alpha_{00} + \gamma_{00})$  in equation (1) represents the level of the outcome variables in the absence of the intervention ( $Intervention_i = 0$ ) at 6-month follow-up ( $Time_t = 0$  and  $(Time_t - t^*) = 0$ ). The term  $\omega_{0i}$  denotes the participant-specific random effect,  $\epsilon_{0j}$  the site-specific random effect, and  $\varepsilon_{itj}$  denotes the

residual error term.  $X_i$  includes the baseline measure of the outcomes to control for severity of the outcome at baseline. We also estimated the effect of the intervention six months after it ended, i.e., 12-months after baseline, using the time-by-intervention interactions. Given  $Time_t = 6$  for the 12-month follow-up and  $t^* = 6$  since PMSB lasted six months, the intervention effect evaluated 12 months after baseline is given by  $\beta_1 + \beta_2 \times 6 + \beta_3 \times 6$ .

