In assessing the effectiveness of PMSB on physical function outcomes (SPPB (8), LLFDI and WHODAS 2.0 (9)), 35 participants in the intervention condition were excluded from the analysis because they could not receive the Strong Bodies treatment due to lack of medical clearance (9 participants), death (2 participants), medical condition (e.g., surgery, knee replacement; 5 participants), lack of access to facilities following the hurricanes in Florida and Puerto Rico (18 participants), or they had to be referred to treatment due to active suicidality (1 participant). Their control counterparts, according to the 2-person block randomization, were also excluded to rebalance the sample. We applied this exclusion because the lack of sessions in Strong Bodies was not related to the intervention but to these other external factors. In total, 70 participants were excluded in all analyses where the outcomes were physical function measures. We confirmed that baseline characteristics between control and intervention participants remained balanced after this exclusion.

We conducted four sets of sensitivity analyses. First, to account for multiple outcome assessment, we estimated a multivariate multilevel regression (10) to test treatment effects obtained from a joint model instead of modeling the outcomes separately. This strategy accounts for the correlation among outcomes and provides more powerful tests of treatment effects compared to more traditional approaches (e.g., Bonferroni adjustments or combining the outcomes into a composite measure)(11). To estimate this multivariate model, we created a long data set where each outcome (SPPB, LLFDI, WHODAS 2.0, HSCL-25 and GAD-7) at each follow-up assessment (2-, 6-, and 12-months) was stacked for each individual, meaning a data set where each participant had 15-observations (five outcomes times three follow-up assessments). The values for each outcome were combined into a single outcome variable  $Y_{hitj}$ , where  $h$  indexes the outcome measure. Instead of estimating equation (1) separately for each outcome, we produced a single equation

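### The secondary compliance analysis cannot confirm the intent-to-treat result or size the intervention effect: it compares participants by sessions received, with no stated method for selection into attendance

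*Combined protocol and SAP*

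**What the plan says.** The last paragraph of Analytical methods uses the count of sessions received as the exposure, in three levels. The lowest is "categorized as compliance equal to zero (control group or intervention participants with no PM and no SB sessions"). The middle level is some sessions of either component but short of full. Full compliance is 10 Positive Minds and 25 to 36 Strong Bodies sessions.

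The plan grants that random assignment no longer underpins the comparison. The same sentence then states that "it serves to provide confirmation of the results from the intent-to-treat analysis". It goes on to a second use, which is that the compliance model "provides further estimates of the magnitude of the intervention effects on the main outcomes evaluated at 6 and 12 months after the baseline".

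On the analysis set, "all compliance analyses excluded the 35 participants who did not receive the SB sessions and their 35 control counterparts".

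On adjustment, the compliance model is not written out. In the primary equation (1), the covariate term "includes the baseline measure of the outcomes to control for severity of the outcome at baseline", and there are random intercepts for participant and site. The sensitivity analyses add race/ethnicity, language or clinical site, or baseline service use or severity. The compliance paragraph does not say which of these terms it uses.

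**The concern.** How many sessions a person attends is settled after randomisation and may depend on how that person is faring or is likely to fare. If it does, full attenders would differ from controls even under an inert intervention. Adjusting for the baseline outcome removes only the part of that difference that baseline predicts.

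Two uses of the analysis are then at stake. Agreement between the compliance contrast and the intent-to-treat estimate is not confirmation, because selection alone can produce it. The coefficients for some and full compliance are not effect sizes of the intervention, because they mix effect with selection in unknown proportion. A reader who takes the sentence at face value could cite a non-randomised contrast both as corroboration and as a dose-response magnitude.

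**Working it through.** The plan gives no figure to reproduce here beyond the counts, so those come first.

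**1. Analysis set** (Analytical methods, exclusion for the physical-function outcomes)
- Reasons for exclusion: 9 + 2 + 5 + 18 + 1 = 35, as stated.
- With control counterparts: 2 × 35 = 70, as stated.
- Remaining: 307 − 70 = 237.
- Health-related reasons (clearance, death, medical condition, suicidality): 9 + 2 + 5 + 1 = 17. The other 18 are hurricane-related loss of facilities.

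**2. Mechanism, with a true effect of zero**

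Assumptions, none of them in the documents: arms of 118 and 119; a standard normal attendance propensity with correlation ρ to the part of the outcome not explained by baseline; a top fraction p of the intervention arm fully compliant; every other intervention participant attending something.

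Controls have mean propensity 0, so the spurious full-versus-zero contrast in residual SD is ρ × c, with c = φ(z)/p, where z cuts off the top fraction p.
- p = 0.30: c = 0.3477/0.30 = 1.159.
- p = 0.50: c = 0.3989/0.50 = 0.798.
- Lowest case: 0.1 × 0.798 = 0.08. Highest: 0.3 × 1.159 = 0.35.

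At ρ = 0 the contrast is zero. At negative ρ it changes sign. Simulated null trials (4,000 per setting, adjusted for baseline) agree: 0.076 and 0.344 at these two extremes, and −0.348 at ρ = −0.3 with p = 0.30.

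**3. Does it depend on pooling non-attenders with controls?**

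If 10% of the 118 attended nothing, 11.8 people with mean propensity −1.755 join 119 controls. The zero-group mean falls by (11.8/130.8) × 1.755 = 0.158, so c becomes 1.317 or 0.956. The range moves only to about 0.10 to 0.39. The point stands without pooling.

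**4. Effect on inference**

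A second simulation (2,000 null trials per setting, N = 237, baseline–outcome correlation 0.6, intervention arm split 10/50/40% into zero, some and full) gives, in total outcome SD:

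| ρ | Full-versus-zero contrast | Rejection at nominal 5% |
|---|---|---|
| 0 | 0.00 | 4.8% |
| 0.1 | 0.09 | 9.2% |
| 0.2 | 0.18 | 25.8% |
| 0.3 | 0.27 | 52.2% |

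Check at ρ = 0.3: residual SD = √(1 − 0.6²) = 0.8 and c = 0.966 + 0.158 = 1.124, so 0.3 × 1.124 × 0.8 = 0.27. Across all settings run, the regression on randomised arm stayed near zero, with rejection between 4.6% and 5.6%.

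Both exercises use one time point, no site effects and no imputation. Since ρ is an input, they show what selection would do, not that it occurred.

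**The case against.** The analysis is labelled secondary, the loss of randomisation is disclosed in the same sentence, and nothing in it alters the intent-to-treat estimate. All of that stands and limits the seriousness of the point. It does not rescue the two claims: the disclosure removes the basis for them and nothing is put in its place.

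Four stronger readings are tempting, and the documents do not support them.
- A reader might infer that baseline outcome was the only adjustment ever considered. The sensitivity analyses name other covariates, and the public text leaves open which entered the compliance model. Tables outside that text may say.
- A reader might infer from the 17 health-related cases that attendance was in fact selected on health here. All 17 are removed from this analysis, and the plan's reason for removal is that "the lack of sessions in Strong Bodies was not related to the intervention but to these other external factors". They show that health can affect receipt. No later drop-off for similar reasons is reported among the 237.
- A reader might take 0.08 to 0.35 SD as the bias in this trial. It rests wholly on assumed inputs; the documents give neither an attendance distribution nor a link between attendance and prognosis.
- A reader might treat the zero category as defective. If the 35 are only the externally caused cases, the definition is coherent and other non-attenders sit with controls. How many there are is a missing detail, and the point does not need it.

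**Conclusion.** The stated inference does not follow. The comparison is by a post-randomisation exposure, no method for selection into attendance is stated, and so it can neither corroborate the intent-to-treat result nor estimate the size of the intervention effect. This conclusion rests on logic and needs no assumed number. It would fail only if attendance were unrelated to prognosis after whatever adjustment was made, and the plan offers no ground for that.

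The size and direction of any bias in the 237 are unknown. The effect on the trial is confined to how this secondary analysis is interpreted, so the correction is worth making but does not touch the primary comparison.

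**What to change.** **Wording.** Delete the statements that the analysis confirms the intent-to-treat result and estimates the magnitude of intervention effects. Label the three-category comparison associational and non-causal. This costs two clauses and a label. It would help, as reporting detail, to name the covariates, give counts by category, and say whether home exercise counts as a session for those who "received training from their Exercise Trainer to use the instructional video and perform the exercises at home".

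**If an effect of treatment received is wanted.** Replace the comparison with a complier-average causal effect of any session received, at 6 and 12 months, in all 307 participants, with randomised arm as instrument and adjustment for the baseline outcome. State the exclusion restriction (assignment affects outcome only through receiving a session). State how outcomes after death are handled, since the two deaths among the 35 return to the set. Present the result as a rescaled intent-to-treat effect. For the physical-function outcomes, show the 307-participant intent-to-treat estimate beside it, because the plan analyses those without the 70.

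**Cost of that option.** One more model per outcome and a wider interval. The standard error grows by about 1/uptake. Assume arms of 153 and 154, and 10% non-attendance among the 153 − 35 = 118 other intervention participants, so 106.2 attend.
- All 35 had a Positive Minds session: uptake (106.2 + 35)/153 = 92.3%, ratio 1/0.923 = 1.08.
- None did: uptake 106.2/153 = 69.4%, ratio 1/0.694 = 1.44.

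With 0% non-attendance the ratio runs from 1.00 to 1.30, and with 20% from 1.18 to 1.62. The estimate does not give the effect of full compliance, and its exposure mixes Positive Minds alone with both components.
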